After informed consent, each subject will undergo a complete physical examination by a physiatrist board certified in SCI medicine ([name] or [name] or [name]), including neurologic assessment and American Spinal Injury Impairment Scale Classification (AIS) examination. Participants will be evaluated every 3 months after treatment initiation and then annually to assess any adverse effects and to check compliance. Testosterone measurements will be acquired every 4 weeks during the intervention to determine the serum level and the dose will be adjusted to allow ~30% increase from baseline ([name]). A prostatic abnormality on digital rectal examination will also lead to exclusion. An increase in serum or plasma prostate specific antigen (PSA) of 1.4 ng/ml above baseline will result in immediate cessation of TRT.

Measurements. All participants will undergo body composition assessments (**specific aim 1**), metabolic studies (**specific aim 2**) and muscle biopsies (**specific aim 3**). All testing procedures will be conducted one week prior to training (**baseline**), 6 months following training (**mid-intervention**) and one week after the end of 1 year of training (**post-intervention**). At each time point, measurements will include estimation of body composition, anthropometry, and dual x-ray absorptiometry (DXA). MRI scans will be obtained for thigh skeletal muscles to determine IMF and CSA.¹⁴⁻¹⁸ Participants will remain at the VA Medical Center for dinner, and overnight. After an overnight fast the subject will be gently awakened at 6 AM to measure BMR. At 6.30 AM an IV line will be placed and blood will be drawn for serum total T and IGF-1 concentrations at 6.30, 7.00 and 7.30 AM. Resting blood pressure and fasting metabolic markers will be obtained

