¹⁸ The skeletal muscle CSAs will be determined at baseline, 6 months (mid-intervention) and 1 year after training (post-intervention). Both lower limbs will be strapped together using a soft Thera-band to avoid any movement inside the magnet. Participants will be instructed to lie still inside the magnet and they will be provided with earplugs to protect their ears against the magnet noise. The duration of the whole scan including the preparation time should not exceed 10 minutes. Images of both thighs will be collected using the following scanning parameters (repetition time, 500; echo time, 14; field of view, 20cm; matrix, 256×256). Transaxial images, 8 mm thick and 4 mm apart, will be taken from the hip joint to the knee joint using a localized coil. Images will be downloaded and analyzed using X-vessel software.^{17,19,20, 31,55}

Testosterone and PSA Concentration. The serum testosterone concentration and PSA levels will be measured at the beginning, every 4 weeks and 1 year after intervention. IV line will be placed after overnight fast, serum total T and PSA concentrations will be measured in duplicates.⁷⁸ Samples will be sent for analysis using a standard procedure assays.

Specific Aim 2. We will determine the association between the changes in skeletal muscle size, IMF, leg lean mass and the metabolic profile as determined by measuring basal metabolic rate (BMR), lipid panel and carbohydrate profile. Participants will undergo an array of metabolic measurements at baseline, 6 and 12 months post-interventions including BMR, fasting lipid panel and 3 hour IVGTT. Other metabolic and inflammatory biomarkers (plasma IGF-1, IGFBP-3, TNF-alpha, IL-6 and CRP) will also be measured at the 3 time points. We hypothesize that the increase in lean mass following TRT+ LPWS will increase BMR and improve both carbohydrate and lipid profiles as well as associated with decrease in FFA and inflammatory biomarkers.

BMR and respiratory exchange ratio. After an overnight fast, participants will be kept in a dark room for 20-30 minutes to attain a resting state during which BMR will be measured by using a canopy. The gasses (VCO₂ and VO₂) collected will used to determine the respiratory exchange ratio. This will help to determine the changes in the percentage of substrate utilization (% fat vs. % carbohydrate) after the interventions.¹⁵

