[name] will clinically and medically supervise all our participants during the course of the study. Possibility of skin rashes will be treated with glucocorticoid cream after removal of T patches. The PI will supervise all the participants closely and provide a weekly call to identify any issues. Participants will be monitored for any changes in baseline health. Participants will undergo blood work to determine serum T-level as well as their Prostate-specific antigen (PSA). There is no specific normal or abnormal level of PSA; however, a value above 1.4 ng/ml or increase of the PSA above 1.4 compared to baseline values will result in immediate cessation of TRT. We will also check the HCT every 4 weeks to ensure that hematocrit (HCT) is less than 54%, value greater than 54 may result in polycythemia.

Moreover, a staff physician who is board certified in SCI medicine will evaluate all participants who enroll in the study. This physician is competent to assess for urologic irritative or obstructive voiding symptoms and for changes in erectile function. This is a routine component of SCI medicine practice for patients with urologic symptoms related to both neurogenic voiding dysfunction and prostate hypertrophy. The physician will assess each participant for new symptoms every three months.

Study removal criteria may include:

- Extensive skin irritation or rashes or itching as result of TRT applications
- Medical history of carcinoma of the breast, carcinoma of the prostate, venous thromboembolism, pulmonary embolism, stroke, cholestatic jaundice, hypertension, serious heart problems, heart failure, myocardial infarction, ventricular arrhythmia, exertional chest pain, insulin dependent diabetes, hypercholesterolemia, hypertriglyceridemia, impaired liver function, or significant renal dysfunction.
- cardiovascular events similar to acute myocardial infarction, acute coronary syndrome, congestive heart failure, any cardiovascular-related hospitalization, stroke, or cardiac arrest, and the development of new significant ischemic findings or symptoms during the course of

the study (including development of new major abnormalities on serial EKGs or symptoms of typical angina)

- Serum PSA >4.0ng/ml
- Increase in serum PSA of >1.4ng/ml compared to baseline
- HCT >54%
- Liver enzymes (AST / ALT) >1.5 times normal upper limit
- Hemoglobin >17.5 g/dL
- Serum calcium between 10.5 11.2mg/dL with symptoms of hypercalcemia
- Gynecomastia

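### Sections 4 and 7 give different PSA triggers for the same mandatory stop of testosterone, and entry screening states no numerical PSA limit

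*Combined protocol and SAP*

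**What the plan says.** **Stopping TRT.** Section 4 (Research Design and Methods), in the paragraph on the physical examination that follows the exclusion criteria, states: "An increase in serum or plasma prostate specific antigen (PSA) of 1.4 ng/ml above baseline will result in immediate cessation of TRT". It gives no absolute PSA value. Section 7, under protection from risk associated with TRT, states that "a value above 1.4 ng/ml or increase of the PSA above 1.4 compared to baseline values will result in immediate cessation of TRT". The same sentence opens with "There is no specific normal or abnormal level of PSA".

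**Study removal.** A list later in that part of Section 7 is introduced by "Study removal criteria may include". It contains "Serum PSA >4.0ng/ml" and "Increase in serum PSA of >1.4ng/ml compared to baseline". This concerns leaving the study and is worded as discretionary.

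**Entry.** Neither the Section 4 exclusion paragraph nor the numbered exclusion list in Section 5 contains a PSA value. The related safeguards are:
- Section 4, physical examination paragraph: "A prostatic abnormality on digital rectal examination will also lead to exclusion".
- Section 4, testosterone replacement therapy: PSA is checked for normality against an outside guideline, with no number given.
- Section 5, exclusion list, item 2: the site physician may exclude for other medical conditions.
- Section 5, informed consent process: the primary provider gives written medical clearance before a man is approached.

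**Testosterone level (minor note).** Section 4 adjusts the dose towards a rise of about 30% from baseline. The TRT paragraph of the same section calls for patch re-education when the rise is below 250 ng/dL. Men with baseline testosterone above 800 ng/dl are excluded.

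**The concern.** A mandatory, immediate stop of a study drug should have one trigger that all staff apply in the same way. Here the same PSA result can meet the stop in one section and not in the other. The absolute limb in Section 7 takes no account of baseline, so a man can meet it on the day he enters, with no change in PSA. It also fits poorly with the opening words of its own sentence.

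What is at stake is consistent handling of a safety rule and of exposure to TRT, which both arms are to receive for one year. The rule is applied repeatedly, because PSA is measured at the start and every 4 weeks.

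**Working it through.** **Inputs.** Let b be baseline PSA and v a later value, in ng/ml. The documents give no PSA distribution, so the values of b and v below are illustrative assumptions.
- Section 4 rule: stop TRT if v − b reaches 1.4.
- Section 7 text: stop TRT if v > 1.4 or v − b > 1.4.
- Section 7 removal list: possible study removal if v > 4.0 or v − b > 1.4.

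**Step 1: trigger points.** Section 4 acts at b + 1.4. Section 7's text acts just above 1.4. The difference is (b + 1.4) − 1.4 = b.

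| Baseline b | Section 4 | Section 7 text | Gap |
|---|---|---|---|
| 0.5 | 1.9 | 1.4 | 0.5 |
| 1.0 | 2.4 | 1.4 | 1.0 |
| 2.0 | 3.4 | 1.4, already exceeded at entry | 2.0 |

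**Step 2: the same result under each text.**

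| b to v | Rise | Section 4 | Section 7 text | Removal list |
|---|---|---|---|---|
| 1.0 to 1.5 | 0.5 | not triggered | stop TRT | not met |
| 2.0 to 2.0 | 0 | not triggered | stop TRT | not met |
| 3.0 to 4.1 | 1.1 | not triggered | stop TRT | met (absolute value) |
| 0.5 to 1.95 | 1.45 | stop TRT | stop TRT | met (rise) |

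**Step 3: all sentences applied together.** PSA cannot be negative, so b ≥ 0.
- If v − b > 1.4, then v > 1.4 + b ≥ 1.4. The rise limb in Section 7's sentence can therefore never add a case to its absolute limb.
- If v − b ≥ 1.4 (Section 4) and b > 0, then v ≥ 1.4 + b > 1.4. Section 4's rule is then covered as well. The one exception is b = 0 with v exactly 1.4, because Section 4 says a rise of 1.4 and Section 7 says above 1.4. It has no practical weight.

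On the cumulative reading the operative rule is simply v > 1.4, and both rise criteria for stopping TRT are idle.

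**Step 4: entry.** None of the four safeguards listed above carries a PSA number. A stable value above 1.4 is therefore not clearly excluded, and it meets Section 7's stop at b with v = b.

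**Step 5: testosterone, minor note.** The document's unit pair for 1000 ng/dL is 34.7 nmol/L, so 250 × 34.7/1000 = 8.675. This reproduces the stated 8.7 nmol/L, so 250 is not a misprint. An exact 30% rise is 0.30 × 300 = 90, 0.30 × 413 = 124 and, at the entry cap, 0.30 × 800 = 240 ng/dL. All are below 250. The break-even baseline is 250/0.30 = 833, above the cap. Even at 35% it is 250/0.35 = 714, so only men with high baselines would clear the flag. For context, the preliminary data report a mean change from 413 to 525 ng/dl in the NMES+TRT group: 112, or 112/413 = 27%. That trial used 2–6 mg daily and excluded men who did not respond to NMES.

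**The case against.** The strongest reply is that the two rules differ in scope and do not clash. Section 4 gives one sufficient trigger. Section 7 repeats it, apart from the boundary value, and adds a second. Neither tells anyone to continue TRT when its own trigger is absent, so both can be obeyed at once by stopping above 1.4. That much stands: a reader might infer that the sections issue orders that cannot both be followed, and the documents do not support that. The reply does not make the text sound, however. Obeying both empties the rise criteria of effect and allows a mandatory stop at entry with no change in PSA. A drafter who meant that rule would have had no reason to write a rise criterion in either section.

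A reader might also count the removal list's 4.0 ng/ml as a third TRT-stopping limit. It is not: it governs a different action, and its wording is discretionary. Stopping a drug and then deciding on removal are compatible. That the protocol does not spell out how the two relate is a missing detail rather than an inconsistency.

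A third stronger reading is that men enter with no PSA safeguard at all. The guideline-based check of PSA in Section 4 and the clinical safeguards in Sections 4 and 5 rule that out. The removal list also includes medical-history items, so parts of it may bear on entry. What remains is that no PSA number is stated for entry, and whether the outside guideline would exclude a given man cannot be settled from these documents.

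**Conclusion.** The point holds as a difference between two written triggers for one mandatory action, most plausibly a drafting error in the absolute limb, the rise limbs or both. The trigger points differ by exactly the baseline PSA. This rests only on the wording of the two sections and on PSA being non-negative.

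The size in participants is unknown, because no PSA distribution is given. A reader might infer bias between arms or damage to the muscle-size result. The documents do not support either: both arms receive TRT under the same PSA rules, and nothing ties the PSA rules to arm. The text under the Data Safety and Monitoring Board heading was not available to me, so any PSA rule there should be checked too.

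The testosterone mismatch is real but minor. Every man exactly on the 30% target is flagged, and the only consequence is patch re-education. Compliance is checked separately by patch inventory.

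**What to change.** The sponsor should reconcile the physical examination paragraph of Section 4 with the TRT risk text of Section 7, so that stopping TRT has one PSA criterion, worded identically wherever it appears. That criterion should be consistent with entry screening (the exclusion lists in Sections 4 and 5 and the guideline-based PSA check in Section 4) and with the separate, discretionary removal list in Section 7. Which criterion to adopt is a clinical decision, and no threshold is proposed here.

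In the same amendment, the testosterone target and the re-education flag in Section 4 should be made consistent with each other.

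The cost is a wording amendment. No new tests are needed, since the plan already provides that "The serum testosterone concentration and PSA levels will be measured at the beginning, every 4 weeks and 1 year after intervention".
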